### **Statistical analysis:**

Power analysis (using G power 3.1 software) shows that a sample size of 50 subjects with ASD receiving 4 different treatments is needed to reliably detect (95% power) effect sizes small or larger (Cohen's  $d=0.2$ ) on one measure. In this study, we expect to find small to medium size effects of oxytocin inhalation on behavioral measures (based on previous meta-analysis of Bakermans-Kranenburg and Van I Jzendoorn. 2013). Authors found a combined effect size of  $d=0.32$  (95% confidence interval: 0.18-0.47). As mentioned above, we are planning to break the blind with  $N=25$  ASD subjects for a mid-way analysis, which is sufficient to detect effect sizes between medium and small (Cohen's  $d=0.3$ ). We expect larger effect sizes on measures of brain

activity (BOLD activity and functional connectivity). Therefore, these measures will be mainly analyzed during the mid-way analysis for potential publications. Of note, we are also planning to publish the combined analysis with the total number of subjects on the measures that were published mid-way to avoid any publication bias.

For healthy subjects, we need at least 30 subjects receiving on treatment to reliably detect (95% power) the differences between social and non-social conditions or emotional faces versus neutral faces in the aims above with an effect size between small and medium (Cohen's  $d=0.35$ ).

When comparing healthy subjects to patients with autism (placebo administration only), the above numbers are sufficient to reliably detect small effect sizes between groups (Cohen's  $d=0.2$ ) for one measure.

The PI will submit an annual report to the IRB and address whether the study is safe and whether it is appropriate to continue. This report will include compliance, review of eligibility, treatment review, summary of responses, survival, adverse events and safety monitoring rules.

Given that we do not expect serious adverse events and we are investigating the effects of this hormone on brain activity and behavior, we do not expect an early stopping.

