There will be analysis at various stages of the trial. We might need to analyze the behavioral and physiological data for data monitoring committee, in any or to write reports to NIH about the progress. There will be analysis of primary outcome measures of the different aims (cited above) during mid-way analysis (when we break the blind half way at  $N=25$  of ASD). The analysis will also be conducted at the final stage of the trial.

Brain imaging procedures using MRI, fMRI will be conducted at the Biomedical Imaging Technology Center (BITC) at Emory. Anatomical Image Acquisition: participants will be positioned supine in the MRI scanner (Siemens, Magnetom Prisma, Trio 3T) with instructions to lie motionless. Padded head restraint will minimize head movement during scanning sessions, each of which will begin with a 15 second scout scan to localize the position of the brain within the magnet. This will be followed by T1-weighted MPRAGE scan (TR= 2300 ms, TE = 4 ms, matrix = 256x256, FOV=256, slice thickness = 1.00 mm, gap = 0 mm).

**For aim 1, the primary outcome measure** consists of investigating the effects of different treatments (3 doses of oxytocin and one dose of placebo) on brain functional connectivity at rest in patients with ASD, using fMRI. During resting state functional image acquisition (8 minutes), participants will be asked to remain awake and not moving. Image acquisition will be obtained using a multi-band slice accelerated gradient echo-planar imaging (EPI) pulse sequence 179, 180 with the following parameters: TR = 1000 ms, TE = 24 ms, matrix = 74 x 74, FOV = 220 mm, slice thickness = 2.0 mm, 64 axial slices, to reduce magnetic susceptibility artifact in the OFC region.

The aim of this analysis is to determine whether there is target engagement for intranasal oxytocin by demonstrating differences between doses of IN-OT on BOLD rsFC or whether there is a simple oxytocin effect. We define target engagement OXT effect (TEE-OXT) as any differential effect between a dose of OXT from another dose of OXT on brain or behavior. We define oxytocin effect

(OXT-Effect) as any differential effect between oxytocin (any dose) and placebo administration in ASD.

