Initial preprocessing steps for single-subject resting-state fMRI data will be conducted with FSL software or SPM with the help and training of [name]. fMRI data will undergo standard preprocessing steps: realignment, slice-timing correction, volume registration, spatial normalization to MNI152 template, spatial smoothing with 5 mm FWHM Gaussian filter and temporal band-pass filtering (0.01-0.1 HZ). Corrections for head motion, whole-brain signals, ventricular signals, white matter signals. We will define specific regions of interest that includes the social brain network that we discussed in the sections above (MPFC, OFC, PCC, precuneus, insula, ACC, ventral striatum, amygdala, temporal areas, SMA etc). We will compare the functional connectivity between and within the different social brain networks (including the default, the salience network and temporal network) between the different treatment conditions. This analysis will be performed based on the GLM using corresponding regressors. We will also compute the rsFC between the different regions of interest by calculating a Pearson's correlation coefficient between the time series of the preprocessed functional MRI signals. In order to study target engagement effect on within network correlations, the resulting of the cross-correlation maps will be Fisher transformed to z-scores and fed into a 2-factor (4 treatment condition X 3 networks (default, salience, temporal); covariate: visit order) ANOVA. In order to study target engagement effect on between network correlations, the resulting of the cross-correlation maps will be Fisher transformed to z-scores and fed into a repeated Anova (4 treatment condition X 3 networks (Salience+Default; Salience+Temporal; Default+Temporal); covariate: visit order) ANOVA. In order to determine simple oxytocin effect, T-contrast maps will determine the differences in rsFC between placebo and each of the different doses of oxytocin. Multiple comparison correction will be conducted. The specificity of the results will also be conformed in a whole brain analysis. Given that baseline rs-FC is not acquired, and in order to account for non-specific fluctuations, we will use a two-stage GLM procedure during which we account for within-subject variability (across the different visits). Time regressor will be added to the model as a covariate to control for external factors that could influence rs-FC other than the treatment.

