*The secondary outcome measure* consists of correlating the effects of treatments on rsFC with the clinical improvements following treatments and post scan in ASD. The variables consist of BB-CGI clinical score (that will be rated blindly by a physician) and a socio-emotional behavioral score (rated by PI or staff blindly) during the BB-CGI. These two variables will be analyzed separately as they are dependent (based on the same test) but answer two different questions. We will conduct correlation analysis (Spearman or Pearson) between TEE-OXT or OXT-effect on rsFC and behavioral and clinical improvements. Behavioral variables will include: emotional responses, gestures, eye contact with experimenter and synchrony).

**For aim 2:** *The primary outcome measure of the second aim* consists of investigating the differences between the effects of the different treatments on BOLD activity of socio-emotional brain regions in response to social cues (Face perception task) in ASD. ROI analysis will include regions such as inferior occipital cortex, fusiform gyrus, superior temporal cortex, intra-parietal sulcus, superior parietal lobule, nucleus accumbens, amygdala and OFC). In this analysis, we have two variables that we will contrast (BOLD signal in response to emotional faces versus

neutral faces) and 4 treatment conditions within subject design (8IU, 24IU, 48IU and placebo) with covariates (order of visits to control for familiarity effects given that the treatment conditions are completely randomized). The presence of TEE-OXT will consist of finding differences between different treatment conditions of OXT and not only between OXT and placebo. We will also compare each of these OXT treatments with placebo condition separately to study OXT-effect.

*The secondary outcome measure* will consist of studying the effects of different treatments on a behavioral measure that is recorded during the MRI scan of the FPT: visual fixation duration on facial stimuli. Here, we have one variable (duration of visual fixation or eye gaze on emotional and neutral faces) and 4 treatment conditions. We will analyze the data with ANOVA repeated measures for determining TEE-OXT and t-tests for simple OXT-effects.

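### Target engagement in Aims 2 and 3 is any difference between any two doses across eight regions, with no stated correction: about 18% to 34% false claims per set of eight regions with the ANOVA named for Aim 3, about 45% to 65% if dose pairs are tested directly

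*Combined protocol and SAP*

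**What the plan says.** All of this is in the Statistical analysis section of the combined protocol and SAP.

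- **Definitions.** Target engagement (TEE-OXT) is defined "as any differential effect between a dose of OXT from another dose of OXT on brain or behavior". The companion OXT-Effect is defined "as any differential effect between oxytocin (any dose) and placebo administration in ASD". Three active doses give three dose pairs for the first and three dose-placebo pairs for the second.
- **Aim 1.** The network analyses are four-condition ANOVAs. After the dose-placebo contrast maps comes the only correction statement in the section: "Multiple comparison correction will be conducted". It names no method and no family.
- **Aim 2 primary.** Eight regions are named: "inferior occipital cortex, fusiform gyrus, superior temporal cortex, intra-parietal sulcus, superior parietal lobule, nucleus accumbens, amygdala and OFC". They are given as examples, so the list is open. The decision statement is "The presence of TEE-OXT will consist of finding differences between different treatment conditions of OXT and not only between OXT and placebo", followed by "We will also compare each of these OXT treatments with placebo condition separately to study OXT-effect". No test and no correction are named.
- **Aim 3 primary.** Eight regions are named. Target engagement is tested by repeated-measures ANOVA over the four treatments, in two analyses: positive versus neutral feedback, and all faces together. No correction is stated.
- **Timing.** Primary outcomes are analysed unblinded at N=25 and again at the end. Further analytic detail is left to amendments once analysis work begins.

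**The concern.** The plan wants to tell a dose effect (target engagement) from a simple oxytocin effect. Its definition is met by one dose pair differing in one region, and nothing says how many regions or pairs must agree. With eight regions and no stated correction, the chance that something passes by luck is well above 5%. Correction across voxels or clusters within one contrast map would not cover several regions and several dose pairs.

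A second difficulty concerns what the ANOVA tests. A four-condition test that includes placebo can be significant because oxytocin differs from placebo, with the three doses identical. By the plan's own definitions that is an OXT-Effect and not target engagement. At stake is a published dose-response claim that the data do not support.

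**Working it through.** The plan gives no familywise error rate to reproduce. Its power statement (50 patients, four treatments, "is needed to reliably detect (95% power) effect sizes small or larger") is for one measure and does not enter this calculation.

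**Inputs from the plan:** four within-subject conditions; three dose pairs; eight regions per aim; N of 25 (mid-way), 30 (expected) or 50 (target).

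**Assumptions:** two-sided alpha 0.05; exactly eight regions; equal correlation between regions of 0, 0.3 or 0.6; normal data with equal variances.

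**Step 1, independent regions, exact.**
- Direct dose pairs, one region: the chance that the range of three means exceeds 1.96 × √2 on the studentized-range scale is 0.1223. Over eight regions: 1 − (1 − 0.1223)^8 = 0.648.
- One ANOVA per region: 1 − 0.95^8 = 0.337.

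**Step 2, correlated regions.** Simulation with no treatment effect, 6,000 replicates per setting; chance of at least one false finding in eight regions:

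| N | Region correlation | Direct dose pairs | Four-condition ANOVA | ANOVA, then a dose pair |
|---|---|---|---|---|
| 30 | 0 | 64.7% | 33.1% | 25.9% |
| 30 | 0.3 | 60.3% | 30.6% | 24.0% |
| 30 | 0.6 | 46.6% | 23.3% | 18.4% |
| 50 | 0 | 65.6% | 34.8% | 27.0% |
| 50 | 0.3 | 60.0% | 30.7% | 24.4% |
| 50 | 0.6 | 47.1% | 23.6% | 18.0% |

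N=25 gives much the same. The 34.8% is simulation error around the exact 33.7%. So the risk is about 18% to 34% with the ANOVA and about 45% to 65% without it. Counting the dose-placebo pairs as well raises the direct-pair figures at N=50 to 84%, 80% and 66%.

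**Step 3, real oxytocin effect, equal at all doses.** With an assumed difference of 0.8 SD from placebo at every dose, the four-condition ANOVA is significant almost always. The dose pairs behind it are then unprotected, and the false dose-difference rate is 45% to 66%. A smaller common effect opens the gate less often, so the rate falls between this and step 2.

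**Step 4, the remedy.** A 2-df test on the three active doses does not see placebo. At 0.05/8 per region the false-claim rate is about 3% to 5%, both with no effect and with the equal 0.8 SD effect.
- Aim 3 has two analyses. Adjusting each separately gives about 8% to 10%. One family of 2 × 8 = 16 tests is bounded by 16 × 0.05/16 = 5%.
- Counting a hit at either N=25 or the final analysis gives about 6% to 9% on a single contrast.

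**The case against.** The strongest reply is that wherever the plan names a test for target engagement on an outcome, it is an ANOVA: Aim 1, the Aim 2 secondary and Aim 3. A reader might infer that both aims carry the 45% to 65% risk. The documents do not support that for Aim 3, because an ANOVA is named there and roughly halves the risk when nothing has an effect. This part of the reply stands. It does not rescue the plan: 18% to 34% is still several times 5%, and step 3 shows that the protection goes when oxytocin has a large effect common to all doses. The plan expects at least 24IU and 48IU to differ from placebo in Aim 3, so a gate opened by placebo is realistic.

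A reader might also infer an explicit rule that one nominal hit is success. The text sets no threshold and never says tests are uncorrected; it says which contrast counts and is silent on level and family. Nor does it follow that the trial cannot tell a dose effect from noise: effect sizes, directions and consistency across regions remain interpretable, and directional predictions are stated.

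Finally, the plan promises later analytic detail by amendment. That acknowledges the gap, but the detail would arrive once analysis has begun and possibly after the N=25 unblinding.

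**Conclusion.** The concern holds in conditional form. Per set of eight regions, with no treatment effect, the chance of at least one false target-engagement claim is about 18% to 34% under the ANOVA named for Aim 3. It is about 45% to 65% if dose pairs are tested directly, a reading left open for the Aim 2 primary. A large effect equal at all doses brings the ANOVA route back to about 45% to 65%.

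These figures rest on an assumed alpha of 0.05, exactly eight regions and correlations of 0 to 0.6; stronger correlation lowers them. They are not upper bounds, since they leave out the second Aim 3 analysis, the OXT-Effect tests and the N=25 look. The plan should be changed before the analysis is relied on for a dose claim.

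**What to change.** In the Statistical analysis section:

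1. For Aims 2 and 3, define target engagement as a 2-df within-subject test across the three active doses only, in each region of a closed list fixed before unblinding. The open Aim 2 list must be closed first.
2. Adjust by Holm over that aim's regions and, in Aim 3, over both analyses together. Compare dose pairs only in regions that pass, at the same adjusted level.
3. For OXT-Effect, adjust the three dose-placebo contrasts and the regions as one family (3 × 8 = 24 tests for eight regions).
4. For Aim 1, apply the active-dose-only test to the network ANOVAs and state the correction family and method.
5. State alpha. Base the confirmatory claim on the final analysis, and label N=25 results and unadjusted hits exploratory.

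No adjustment across aims is needed. The work is wording and routine code, with no new data. The cost is less power for any single region: the first Holm step is 0.05/8 = 0.00625 in Aim 2 and 0.05/16 = 0.0031 in Aim 3.

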The secondary outcome measure consists of correlating the effects of treatments (whereas the differences between high and low doses or between high and placebo) on rsFC with clinical and behavioral improvements following IN-OT (as compared to small dose or as compared to placebo) in these individuals with ASD. Clinical improvements will be rated by a clinician as a global clinical improvement as based on a videotaped interview (BB-CGI) post scanner. Behavioral improvements will consist of improvements in natural socio-emotional responses (emotional responses and eye contact) during this clinical interview.

**Aim 2: The effects of intranasal oxytocin on the BOLD activity of the social brain network (SBN) in response to social cues (50-60 minutes after IN-OT)**

We hypothesize that IN-OT will enhance the brain activity of regions involved in perception and emotional process in response to morphed emotional faces as compared to neutral faces in subjects with ASD.

Primary outcome measure: The primary outcome measure consists of measuring the difference between treatments in terms of BOLD activity in response to emotional social cues (Face perception task (FPT)). We expect to find that a higher dose of IN-OT will enhance BOLD activity in emotional and perceptual regions known to be active during the perception of emotional face, (inferior occipital cortex, fusiform cortex, superior temporal cortex, intra-parietal sulcus, superior

parietal lobule, nucleus accumbens, amygdala and OFC), as compared to a lower dose of IN-OT or to placebo.

Secondary outcome measures: We will study the effects of the difference between treatment conditions in modulating the visual fixation or gaze duration on the face and eye region of faces during this emotional face test in ASD (measured by the eye tracker inside the scanner). Based on the growing evidence in the literature, we expect to find that higher doses will increase the duration of eye gaze on the face region as compared to placebo and other smaller doses of IN-OT.

**Aim 3: Effects of intranasal oxytocin on the BOLD activity of SBN in response to an interactive social reward task (60-70 minutes after IN-OT)**

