  - **Face Rating questionnaire (post MRI):** participants are asked to rate (on a scale 1 to 7) faces.
  - **A social learning test (SLT):** participants are asked to match faces and words as fast as they can.
  - **Emotion Matching test (EMT):** participants are asked to identify the emotion that is displayed on a face by matching the emotional face that appears on the left to one of the faces that appears to the right (different faces but same emotion).
  - **Toronto Alexithymia scale:** participants are asked to complete a simple questionnaire.
  - **Mood questionnaire (PANAS scale).**
  - **BB-CGI (clinical interview):** the same interview that is performed during the pre-MRI visit will be performed during this visit in order to collect a clinical score of improvement as well as physiological, verbal and socio-emotional improvements.

4- Second, Third and Fourth visit of scan (ASD subjects) (total duration= around 3 to 4 hours each): The exact same procedures will be performed during these other 3 visits. These 3 additional visits will be conducted only in ASD subjects. Also, participants will receive different content of spray (either different dose of oxytocin or placebo).

Of note, the health assessment will be reviewed one more time (in addition to the assessment during the first pre-clinical visit) by the nurse practitioner or the study physician during one of the 4 clinical visits, if the original health assessment expires (more than 30 days).

	Screening and consent review/training	Vital signs 1	Blood samples Pre	Hormone Spray (PL, 8, 24, 48 IN-OT)	Blood samples post	Vital signs 2	MRI scan	Post MRI scan
Visit 1	X	X	X	X	X	X	Rest+ 3 tasks	Quest+ 2 tasks + clinical interview
Visit 2	X	X	X	X	X	X	Rest+ 3 tasks	Quest+ 2 tasks + clinical interview
Visit 3	X	X	X	X	X	X	Rest+ 3 tasks	Quest+ 2 tasks + clinical interview
Visit 4	X	X	X	X	X	X	Rest+ 3 tasks	Quest+ 2 tasks + clinical interview

Table 2: Clinical trial visits for subjects with ASD

Visits will be separated by a one-week interval approximately ( $\pm$  2 to 3 days). We have to be flexible with the scheduling given that we are facing challenges while scheduling all the units and personals. Every patient will receive the 3 doses of IN-OT (8IU, 24IU, 48IU) and placebo in a double blind, placebo controlled trial.

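### The Aim 1 secondary correlation does not say that visit position is removed from the patient-level differences, and no visit term is named for the interview scores

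*Combined protocol and SAP*

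**What the plan says.** All references are to the combined protocol and SAP.

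- **The test.** Under Statistical analysis, the Aim 1 secondary outcome reads: "We will conduct correlation analysis (Spearman or Pearson) between TEE-OXT or OXT-effect on rsFC and behavioral and clinical improvements". The interview (BB-CGI) supplies two variables, a physician-rated clinical score and a staff-rated socio-emotional score. No covariate or partial correlation is named.
- **What is correlated.** Objectives, Aim 1, describes "correlating the effects of treatments (whereas the differences between high and low doses or between high and placebo) on rsFC with clinical and behavioral improvements". The improvements are also defined relative to a small dose or placebo, so both sides are differences between sessions.
- **Design.** The section on the clinical visits says "Every patient will receive the 3 doses of IN-OT (8IU, 24IU, 48IU) and placebo in a double blind, placebo controlled trial", one treatment per visit. The Aim 2 analysis text enters "order of visits to control for familiarity effects given that the treatment conditions are completely randomized".
- **Visit handling for rsFC.** The within-network ANOVA is "4 treatment condition X 3 networks (default, salience, temporal); covariate: visit order", and the between-network ANOVA has the same covariate. The plan adds: "Time regressor will be added to the model as a covariate to control for external factors that could influence rs-FC other than the treatment". Because no baseline scan is taken, it also plans a two-stage GLM to deal with variability across a patient's visits.
- **Visit handling for the interview.** The post-scan list says "the same interview that is performed during the pre-MRI visit will be performed during this visit". With the pre-clinical visit, that makes five administrations. No visit term is named for these scores.

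**The concern.** If a patient has 48 IU at visit 4 and placebo at visit 1, his rsFC difference and his interview difference both span three visits. A patient with the reverse order has both differences spanning minus three. If scores and connectivity change with repetition, the two differences move together across patients even if the drug does nothing.

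Random order does not prevent this. It balances drift in the average dose contrast. It does not remove a component that varies between patients and is common to both sides of a between-patient correlation.

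This correlation is how Aim 1 ties a change in connectivity to clinical improvement. An unadjusted version could show a link that comes from session order. With drifts in opposite directions it could hide a real one.

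**Working it through.** The plan gives no power or error figure for this correlation, so there is none to reproduce. Its power statements concern treatment and group comparisons on one measure. It states no significance level; 5% two-sided is assumed.

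**1. The shared visit gap.** Take all 24 treatment orders as equally likely. For two treatments in four positions, the gap d has |d| = 1, 2, 3 with probabilities 6/12, 4/12, 2/12. It has mean zero and

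E[d²] = (6×1 + 4×4 + 2×9)/12 = 40/12 = 10/3.

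**2. Induced correlation, no drug effect and no true association.** Write the rsFC difference as b₁d + e₁ and the interview difference as b₂d + e₂. Here e₁ and e₂ are independent with unit variance, so b is drift per visit in drift-free SDs of the paired difference. Then

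r = (10/3)b₁b₂ / √[(1 + (10/3)b₁²)(1 + (10/3)b₂²)],

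which for equal drift is (10/3)b² / (1 + (10/3)b²).

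**3. Numbers.** The documents give no drift size, so b is an assumed range. The rates are simulated rejection rates of the Pearson test at N=30, the ASD number that the Randomization and blinding section believes achievable.

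| b, both measures | (10/3)b² | r | neither side adjusted | rsFC side only | both sides |
|---|---|---|---|---|---|
| 0.2 | 0.133 | 0.133/1.133 = 0.12 | 9% | 4% | about 5% |
| 0.3 | 0.300 | 0.300/1.300 = 0.23 | 23% | 3% | about 5% |
| 0.4 | 0.533 | 0.533/1.533 = 0.35 | 49% | 2% | about 5% |

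The smallest |r| significant at N=30 is 0.36.

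**4. Where the effect is small.**
- At b = 0.1, r = 0.0333/1.0333 = 0.03.
- With drift in one measure only, r = 0 and the rate is 5%.
- With b = 0.1 for rsFC and 0.4 for the interview, r = 0.133/√(1.033×1.533), about 0.1, and the rate is about 8%.

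**5. What b means per session.** If session residuals are independent, the paired-difference SD is √2 times the within-visit SD. So b = 0.4 is 0.4×1.414 = 0.57 within-visit SD per visit, or 3×0.57 = 1.7 SD from the first to the fourth session, in both measures. A drift of 0.2 within-visit SD per visit in both measures gives r = 0.06 and a rate of 6% at N=30.

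**6. Does the rsFC adjustment reach the correlation by itself?** One patient has four scans. Four treatment columns plus a visit column make five columns of rank 4, so his own data cannot separate treatment from visit. The visit effect has to be estimated across patients and then subtracted from each patient's values. The plan does not describe that step.

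**7. Limits of a linear adjustment.** The 5% in the last column assumes linear drift. With front-loaded habituation, linear adjustment of both sides leaves r of about 0.05 and a rate of about 6%. If patients have their own drift slopes and these correlate between measures, adjustment for a common visit effect left r of about 0.06 and a rate of about 7% in the case tried.

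**The case against.** The best reply is that the rsFC effect to be correlated is the one estimated by the preceding rsFC model, which has visit order, a time regressor and a two-stage GLM. On that reading a common linear drift cannot create the correlation, even with raw interview scores. This stands as a possible reading, and it limits the point: the plan leaves the matter open. It does not close it, because a covariate in a group model does not by itself alter the differences passed to a separate correlation (step 6). Even when it does, the interview difference keeps its visit variance and the test is conservative.

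A reader might infer that the plan ignores visit position altogether, or that a significant correlation would probably be an order artefact. The documents do not support either. The familiarity and habituation remarks belong to the Aim 2 face task and the Aim 3 ball game. The Introduction describes resting connectivity as stable across sessions. The pre-clinical visit already includes a scanner habituation session and a first interview, so first exposure falls outside every difference compared. Nothing states that interview scores drift.

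The planned 50 patients would raise the unadjusted rates to 13%, 36% and 72%. Those figures look less applicable: the healthy-subject screening section says ASD testing is already complete, and the text elsewhere expects about 30.

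Finally, the plan promises to check confounders and covariates and to add analysis detail by amendment. That leaves room for the fix but does not supply the term.

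**Conclusion.** The point holds as a gap in specification with a cheap remedy. The correlation is written without a visit term, the carry-over of the rsFC adjustment to patient-level differences is unstated, and the interview scores have no adjustment at all.

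If unadjusted differences are used, the 9% to 49% rates at N=30 apply only under same-direction linear drift in both measures of 0.2 to 0.4 paired-difference SDs per visit. The documents do not show drift of that size. With small drift, or drift in one measure, there is little or no inflation. If only rsFC is adjusted, false positives fall to about 2% to 4%, so the cost is some sensitivity. The documents do not establish that the planned result would be biased.

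**What to change.** In the Aim 1 secondary outcome paragraph of Statistical analysis, replace the plain correlation with one of these:

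- Remove visit effects, with visit as a four-level factor estimated across patients, from rsFC and from the BB-CGI and behavioural scores. Then form each patient's differences and correlate them.
- Use a partial correlation (Pearson or rank) adjusted for the visit positions of the two sessions compared.

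A single linear term for the visit difference is a simpler approximation and is not equivalent to the factor, since it leaves a small residue if habituation is front-loaded. No adjustment for a common visit effect removes correlated patient-specific slopes, and one sentence should acknowledge this.

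The cost is a sentence or two and one to three degrees of freedom. The adjustment uses only the visit order that the imaging models already need, so no new data are required.
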